6.2.4 NELLIX POLYMER DISPENSER

The Nellix Polymer Dispenser is a hand-held, re-useable (NP-001 or NP-003) or disposable (NP-005) device intended to actuate delivery of the mixed polymer solution at the time of use (**Figure 16**).

FIGURE 16: REUSABLE DISPENSER (LEFT) AND DISPOSABLE DISPENSER (RIGHT)

6.3 OVATION IX ILIAC STENT GRAFTS

The Endologix Ovation iX Iliac Limb and Iliac Extension Stent Grafts (Ovation iX Iliac Stent Grafts) used in the ChEVAS System are identical to the commercially available Ovation iX Iliac Stent Grafts currently approved via P120006/S015. No changes were required to the Ovation iX Iliac Limb and Extender Stent Grafts or delivery system for use as part of the ChEVAS System. The Ovation iX Iliac Stent Grafts are used to establish or re-establish the distal seal zone by being deployed into the leg sections of the Nellix Implant. Similarly, the iliac extensions are deployed into the iliac limbs.

The Ovation iX Iliac Limb Stent Grafts (**Figure 17**) are available in straight, flared, and tapered configurations and the Ovation iX Iliac Extension Stent Grafts are available only in a straight configuration. The Ovation iX Iliac Stent Grafts are comprised of a Nitinol stent encapsulated in low-permeability PTFE. The Ovation iX Iliac Stent Grafts are manufactured from polished Nitinol wire and shape set into a sinusoidal pattern superimposed on a helix. The PTFE covering is laminated on both sides of the Nitinol stent. Furthermore, the stent grafts contain radiopaque markers, which enable the physician to visualize both the proximal and the distal ends of the stent grafts.

FIGURE 17: OVATION iX ILIAC LIMB (LEFT) AND EXTENSION (RIGHT)

The Ovation iX Iliac Stent Graft Delivery Catheter (**Figure 18**) is used to position and deploy the Ovation iX Iliac Limb Stent Graft within the Nellix implant and the Iliac Extension within the Iliac Limb, if needed. The Ovation iX Iliac Stent Grafts are constrained over a central guidewire lumen by an integral introducer sheath. The sheath is retracted to deploy the stent graft. After deployment, the delivery system chassis is retracted through the integral introducer sheath.

[figure not shown]

FIGURE 18: OVATION iX ILIAC STENT GRAFT DELIVERY CATHETER

6.4 VERTA SELF-EXPANDING STENT GRAFT SYSTEM

The Verta Self-Expanding Branch Stent Graft System is manufactured for Endologix by Bard Peripheral Vascular, Inc. (Tempe, Arizona; establishment registration number 2020394) and is intended for use solely with the Nellix System in a ChEVAS procedure. Bard Peripheral Vascular, Inc. (BPV) will be the contract manufacturer for the device and is responsible for manufacture, sterilization, labels, and shipping of the device to Endologix. Endologix will receive a finished device from BPV and will not subject the device to any additional processing prior to shipping the device to the investigational sites.

As described in §6.1.1 above, the ChEVAS procedure utilizes the chimney parallel graft technique in order to treat juxtarenal, pararenal, or paravisceral aneurysms. The Verta Self-Expanding Branch Stent Grafts (Verta Stent Graft) are implanted in renal arteries and potentially the SMA, such that the proximal end of

the Verta Stent Graft is parallel to the two Nellix stents in the aorta and the distal end is at least 10mm into the intended visceral artery. The polymer-filled EndoBags conform around the Nellix and Verta stents to seal the aneurysm while maintaining blood flow to the visceral and iliac arteries.

The Verta Stent Graft is a flexible, self-expanding Nitinol stent encapsulated within two layers of ePTFE, the inner (i.e., blood contacting) of which is carbon impregnated. Stent graft diameters range from 6mm to 10mm and the stent graft lengths range from 30mm to 100mm. Each end of the stent graft (Figure 19) has six radiopaque tantalum markers.

[figure not shown]

FIGURE 19: VERTA SELF-EXPANDING BRANCH STENT GRAFT

The Verta stent graft is compressed between the inner catheter and the stent graft sheath at the distal end of the delivery system (Figure 20). The delivery system is an over-the-wire delivery system compatible with 8Fr and 9Fr introducer sheaths, depending on stent graft size, and compatible with 0.035-inch guide wires. The delivery system handle has a deployment mechanism offering two deployment options. The Big Thumbwheel allows for slower deployment of the stent graft for better placement control at the beginning of deployment and the Small Thumbwheel allows for faster deployment of the stent graft once the distal end engages the vasculature. Furthermore, a Safe Lock Slider is included to prevent premature release of the stent graft; the Safe Lock Slider must be unlocked before device deployment.

[figure not shown]

FIGURE 20: VERTA SELF-EXPANDING BRANCH STENT GRAFT DELIVERY SYSTEM

Legend:

A: Atraumatic Tip

E: Catheter Shaft

B: Guidewire Lumen with Luer Connector

F: Safe Lock Slider

C: Stability Sheath

G: Big Thumbwheel

D: Stent Delivery Sheath

H: Small Thumbwheel

The Verta Self-Expanding Branch Stent Graft System is identical to the Covera Vascular Covered Stents (Covera) which has been approved for treatment of stenoses at the venous anastomosis of ePTFE or other synthetic arterio-venous (AV) access grafts under P170042. The only difference between the Verta and the Covera devices are the final labeling of the device and that the Verta device is shipped to Endologix for inclusion as part of the ChEVAS System.

6.5 ADJUNCTIVE STENTS

During treatment of complex aneurysms, the primary clinical objective of the ChEVAS procedure is to seal the aneurysm from blood flow and prevent subsequent rupture; however, the use of additional stents in the visceral arteries may be required to treat common clinical situations that arise within the visceral arteries unrelated to aneurysm exclusion. In the event an additional stent is required, the Verta Stent Graft or the LifeStent Vascular Stent may be used at the physician's discretion based upon positive clinical experience, standard clinical use, and reported benefit to customize patient's treatment.

6.6 PREPARATION/HANDLING/STORAGE/ACCOUNTABILITY

6.6.1 ACQUISITION AND ACCOUNTABILITY

Investigators, or designated personnel, will be responsible for maintaining accurate, complete and current records pertaining to device accountability for any investigational product sent to the site. Device accountability will be tracked for reporting purposes by the sponsor.

The investigational components that will require accountability are the following:

- The Nellix body stents
- The Verta stents
- The Nellix polymer cartridges
- The Nellix polymer dispenser
- The Nellix console
- The Ovation iX iliac limb/extension stents

6.6.2 PRODUCT STORAGE AND STABILITY

The Nellix and Verta stents will be shipped on a case-by-case basis. These must be stored in a secure location. Any unused product must be returned to Endologix. Shipped and returned catheters must be recorded by the site.

The polymer will be shipped to the site on a case by case basis. The polymer will be required to be kept between -40°C and -20°C. This will be delivered in a special packaging that will include a regulator/indicator to ensure adequate temperature during transport and handling. The Case Specialist that will be at the site will have the key and/or combination to the lock on this case. It is important that you remember to log the polymer on the device accountability log (DAL). Unused or remaining polymer may be disposed of per normal hospital protocol (the polymer is non-toxic).

The site will want to inspect the device packaging to verify that no damage has occurred as a result of shipping. If any damage has occurred to the device or the polymer is yellowing, or discolored, do not use the product and contact Endologix immediately.

If needed, the Ovation iX Iliac Stent Graft may be shipped. As with the ChEVAS device system and the polymer, these supplies will arrive STERILE. The site will want to inspect the packaging to verify that there has been no damage as a result of shipping. If there is any damage to the device or the sterility packaging is damaged, contact Endologix immediately.

Any unused investigational devices must be returned to Endologix after completion of the procedure. Waybills for return are included in all packages.

7 STUDY INTERVENTION DISCONTINUATION AND PARTICIPANT DISCONTINUATION/WITHDRAWAL

7.1 DISCONTINUATION OF STUDY INTERVENTION

If an attempt is made to insert one of the ChEVAS System catheters into the subject, the subject is considered enrolled. If the procedure is aborted subsequent to the attempted insertion, the case will be considered a technical failure. The subject will be exited from the study after having completed 30 days of follow-up and recording of all adverse events up until 30 days. A 30-day CT on such a subject is not required.

If a subject is Converted to Open Repair at any time during the study, the subject will be exited from the study after 30 days of follow-up post-surgery.

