3 OBJECTIVES AND ENDPOINTS

3.1 1-MONTH PRIMARY ENDPOINT

The primary 1-month endpoint is defined in terms of an event rate, and includes technical failure and any of the following:

- *Severe Bowel Ischemia* – lack of adequate blood flow to the intestines leading to surgical/endovascular intervention or death and reported within 30 days of the index procedure
- *Permanent Paraplegia/Paraparesis* – event reported within 30 days of the index procedure without resolution at 30 days post-procedure
- *Renal Failure* – new onset renal failure requiring dialysis that remains on-going at 30 days post-procedure
- *Disabling Stroke* – new neurological deficit resulting from vascular insult reported within 30 days of the index procedure without resolution at 6 months post-procedure. Disabling is considered a value of 2 (slight disability) or above on the modified Rankin Scale (mRS) at both the 1-month and 6-month visits.
- *Abdominal Aortic Aneurysm Rupture* - Intraoperative and Post-procedural rupture through the aneurysm wall within the stented segment of the aorta reported within 30 days of the index procedure.
- *Aneurysm-related mortality* - death reported within 30 days of the index endovascular procedure

The technical success component of the endpoint (counterpart to technical failure) is defined as:

- a. Successful access and delivery of all ChEVAS components (i.e., ability to deliver each component to the intended location, without the need for unanticipated corrective intervention related to delivery);
- b. Successful and accurate deployment, defined as:
 - i. Deployment of the Nellix stent-grafts, Ovation limbs, and chimney(s) in the planned location;
 - ii. Patency of the Nellix stent-grafts, Ovation limbs, and chimney(s) with absence of device deformations (e.g., kinks¹, mal-deployment², misaligned deployment³) requiring unplanned placement of an additional device within the endovascular stent-grafts or chimney(s);
 - iii. Adequate seal without the need for unanticipated corrective interventions⁴. No use of components outside the defined ChEVAS System for the purpose of achieving seal. The use of adjunctive stenting for purposes outside of achieving seal or use

¹ Defined as a focal narrowing of the stent lumen of >50%, with concurrent stent wall deformation at that location.

² Defined as concluding the procedure without having all components of the ChEVAS System successfully deployed.

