7.2 PARTICIPANT DISCONTINUATION/WITHDRAWAL FROM THE STUDY

Participants are free to withdraw from participation in the study at any time upon request. The investigator should make it clear to participants that regular follow-up visits are strongly recommended, regardless of study participation, as the subject will still have an implanted investigational device.

An investigator may discontinue or withdraw a participant from the study for the following reasons:

- Significant study intervention non-compliance
- If any clinical adverse event (AE), laboratory abnormality, or other medical condition or situation occurs such that continued participation in the study would not be in the best interest of the participant.

The reason for participant discontinuation or withdrawal from the study will be recorded on the Exit CRFs. Subjects who sign the informed consent form, and receive the study intervention, and subsequently withdraw, or are withdrawn or discontinued from the study, will not be replaced.

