9.3 POPULATIONS FOR ANALYSES

The Primary analysis will be conducted on the implanted population within the ChEVAS Roll-In and Pivotal cohorts. The Intention-to-Treat paradigm is not applied here as this is conventionally applied to two-armed randomized studies. Rather, all subjects receiving an implant are analyzed for the endpoint. The primary 1-year endpoint requires evaluable subjects, so completed cases (subjects who have enough information to be evaluated at 1 year) comprise an additional way to stratify the population. A subpopulation is the per-protocol population, consisting of subjects that have an implanted device, and have not violated the anatomical or procedural IFU criteria. Details of populations are explained further in the SAP.

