The DSMB will provide their recommendations on study conduct as per their review of the study data at Meetings. The recommendations will include but not be limited to, modifications to the protocol, suspension or termination of enrollment, modification of inclusion/exclusion criteria, modification of follow-up scheduling or assessments, or no recommendations on modification. The decision to implement any DSMB recommendations lies solely with the Sponsor.

Events will be followed for outcome information until resolution or stabilization.

For additional training and risk mitigation, all roll-in subjects will have a proctor (physician with prior relevant experience) present during the procedure.

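### Section 7.1 exits aborted cases at 30 days without saying whether this covers subjects with a component left in place, and exits converted subjects 30 days after surgery, so some outcomes needed by 9.3 and 3.3.4 are not collected

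*Combined protocol and SAP*

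**What the plan says.** Section 7.1 sets two exit rules.

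- **Aborted procedures.** "If the procedure is aborted subsequent to the attempted insertion, the case will be considered a technical failure". Then: "The subject will be exited from the study after having completed 30 days of follow-up", with adverse events recorded up to 30 days. It adds: "A 30-day CT on such a subject is not required". The trigger is an abort after attempted insertion; implant status is not mentioned.
- **Open conversion.** "If a subject is Converted to Open Repair at any time during the study, the subject will be exited from the study", 30 days after the surgery.

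Section 9.3 defines the primary population: "Rather, all subjects receiving an implant are analyzed for the endpoint". It does not require a complete implant. It also says that the 1-year endpoint needs evaluable subjects, meaning those with enough information at 1 year.

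The 1-year endpoint in 3.2 counts rupture, aneurysm-related death, open conversion and major device-related re-intervention through day 365, and core-lab imaging findings in the 1-year window only. Table 4 puts that window at days 305 to 425. Technical failure is a component of the 1-month endpoint (3.1) but not of the 1-year endpoint.

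Section 3.3.4 lists all-cause and aneurysm-related mortality among the outcomes collected through 5 years.

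**The concern.** A partial implant is foreseeable from the protocol's own account of the procedure: in section 2.3.4 the chimney stents are deployed before the EndoBags are filled. A procedure abandoned between those steps can leave a covered stent in a renal or mesenteric artery. Such a subject has received an implant, which places him or her in the 9.3 population, yet 7.1 read literally ends observation at day 30.

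If that happens, the 1-year outcome is missing because treatment went badly, so the missingness is informative. Leaving these subjects out of the evaluable set would tend to favour the device in a single-arm test against a fixed goal. In the same way, exit after conversion stops mortality observation in subjects whose device treatment has failed.

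**Working it through.** **1. The plan's own figures.** Inputs from 9.1 and 9.2: performance goal p0 = 0.75, expected rate p1 = 0.857, alpha 0.05 (one-sided, since the hypothesis is success above 0.75), binomial test, 103 evaluable, 14% drop-out.

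The test passes with r or more successes, where r is the smallest integer with P(X ≥ r | n, 0.75) ≤ 0.05.

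- n = 103: r = 85; exact type I error P(X ≥ 85 | 103, 0.75) = 0.0456; power P(X ≥ 85 | 103, 0.857) = 0.855.
- n = 102: r = 85; power 0.798, just under 80%.
- 103 / (1 − 0.14) = 119.8, rounded up to 120.
- 1-month endpoint, n = 120, goal 25%, expected 14.5%: pass with 21 or fewer events; power 0.856.

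These agree with the stated 103, 120 and 85.6%. The sample size is not in dispute.

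**2. Who is affected.** A subject's 1-year outcome becomes unobservable through the aborted-case rule only if all four conditions hold:

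- the procedure is aborted after attempted insertion (7.1 applies);
- a component stays in place (9.3 applies);
- there is no open conversion, which through day 365 is itself a failure under 3.2;
- there is no rupture, aneurysm-related death or major device-related re-intervention before exit.

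The imaging window opens at day 305, so exit at day 30 comes 305 − 30 = 275 days too early. Because technical failure is not a 1-year component, the abort itself does not settle the outcome.

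**3. Size, under an assumption.** The documents do not give the number k of such subjects, so k = 1 to 4 is assumed. Take 103 subjects with a true success rate of exactly 75%, of whom k would all fail and are dropped. The rate among the remaining 103 − k is then 0.75 × 103 / (103 − k), and the type I error is the probability of reaching r at that n and rate.

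| k dropped | n | r | rate among remaining | type I error |
|---|---|---|---|---|
| 0 | 103 | 85 | 0.7500 | 4.6% |
| 1 | 102 | 85 | 0.7574 | 4.3% |
| 2 | 101 | 84 | 0.7649 | 6.7% |
| 3 | 100 | 83 | 0.7725 | 10.3% |
| 4 | 99 | 82 | 0.7803 | 15.1% |

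One dropped subject does not raise the error, because the test is discrete: at n = 102 its exact level with no bias is only 3.0%. Loss of numbers alone matters little. At 85.7%, power for n = 102, 101, 100 and 99 is 0.798, 0.810, 0.821 and 0.832. The issue is bias, not power.

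**4. Effect on a single result.** At the bare minimum pass, 85/103 (p = 0.046), adding one observed failure gives 85/104 (p = 0.067) and adding three gives 85/106 (p = 0.130); both fail. At the design's expected result, 0.857 × 103 ≈ 88, adding one gives 88/104 (p = 0.013), three 88/106 (p = 0.033) and four 88/107 (p = 0.049); all pass.

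**5. Converted subjects.** Conversion by day 365 is a 1-year failure, so that outcome is known. Section 8.5.11 counts death within 30 days of conversion as aneurysm-related, which the exit rule covers. It also lets the Clinical Events Committee attribute other deaths to the aneurysm, and 8.5.10 counts death following a procedure to treat the aneurysm without a time limit. Deaths after exit, from any cause, cannot reach the committee or the 5-year mortality report in 3.3.4.

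**The case against.** The best reply is that 7.1 was written for subjects who leave the procedure with no implant. The waiver of the 30-day CT points that way. This is a plausible reading of intent, but the text does not say so.

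A reader might take footnote 2 in 3.1 as proof that 7.1 expels partly implanted subjects. It does not show that. The footnote defines mal-deployment as "Defined as concluding the procedure without having all components of the ChEVAS System successfully deployed", and a concluded procedure is not an aborted one. Section 3.2 also counts re-interventions for mal-deployed devices through day 365, so those subjects are evidently meant to be followed.

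A reader might also infer a contradiction with 7.2 and 10.1.5. Section 7.2 recommends visits regardless of participation, "as the subject will still have an implanted investigational device", which is compatible with study exit. Section 10.1.5 says "Events will be followed for outcome information until resolution or stabilization", which concerns reported events and does not require scheduled visits. Both are in tension with 7.1 and no more.

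Three further points stand. Table 3 reports 100% technical success in all five ChEVAS series, so few cases are to be expected. Starting from 85/103 is a worst-case choice: at a true rate of 85.7%, a result of exactly 85 has a probability of 7% and one of 85 to 87 has 26%, and every added subject must also fail. And 9.3 and 9.4.2 defer detail to a separate SAP that was not in the text available here. It may define the implanted population or set a missing-data rule, though it cannot recover data that were never collected. On conversion, the loss touches outcomes with no formal test (9.4.3).

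**Conclusion.** The point holds in a narrow form. Section 7.1 does not say whether the 30-day exit covers aborted subjects with a component in place. Followed as written, it would leave members of the 9.3 population with an unobservable 1-year outcome unless a qualifying event had already occurred. The number is unknown and probably small. With one such subject the type I error is not raised; with three or four, all of whom would have failed, it is roughly 10% to 15% instead of 4.6%. Those figures rest on the assumed count, on all of them failing, on a true rate at the goal, and on the subjects being dropped and not imputed.

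The stronger reading, that every aborted case is lost to the 1-year test and that the primary result is biased by design, is not supported. Aborted cases that are converted or have a qualifying event before exit already count as failures, and conversion by day 365 leaves the 1-year endpoint intact. What conversion does cost is later mortality that 3.3.4 undertakes to report. This is a cheap improvement, not a flaw in the sample size or the test.

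**What to change.** Reconcile 7.1 with 9.3, 3.2 and 3.3.4.

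- State that the 30-day exit applies only to aborted subjects outside the implanted population, and that subjects within it remain in study data collection and are counted in the 1-year endpoint.
- For converted subjects, separate study exit from data collection: record vital status and cause of death, by telephone or from records and adjudicated by the Clinical Events Committee, through 5 years.

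The change concerns study data and the analysis set. Clinical and imaging management stays with the sponsor and the investigators.

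The cost is a wording change, a few extra contacts and possibly a slightly lower 1-year success rate.

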7.2 PARTICIPANT DISCONTINUATION/WITHDRAWAL FROM THE STUDY

Participants are free to withdraw from participation in the study at any time upon request. The investigator should make it clear to participants that regular follow-up visits are strongly recommended, regardless of study participation, as the subject will still have an implanted investigational device.

An investigator may discontinue or withdraw a participant from the study for the following reasons:

- Significant study intervention non-compliance
- If any clinical adverse event (AE), laboratory abnormality, or other medical condition or situation occurs such that continued participation in the study would not be in the best interest of the participant.

The reason for participant discontinuation or withdrawal from the study will be recorded on the Exit CRFs. Subjects who sign the informed consent form, and receive the study intervention, and subsequently withdraw, or are withdrawn or discontinued from the study, will not be replaced.

